#### *Dosing Reduction/Discontinuation*

Participants who cannot tolerate or have adverse reactions to Memantine based on the PIs discretion, can chose to terminate the study, reduce their daily intake by 10 mg per day, or can remain on the same study dose for another week. If the AE has not abated, then the PI or patient can again elect to terminate the study, decrease the dose by another 10 mg per day, or remain on the same dose. If the AE is still present, intolerable or medically unsafe after two dose titrations, then the patient must be terminated from the study. If the patient is terminated early, and the patient has not recovered from their adverse events, it must be reported and every effort should be made to follow the patient until the adverse event is resolved. 10mg is the lowest dose the patient can remain on in the study.

When a patient experiences intolerable adverse reactions to a higher dose of medication, we will challenge the higher dose twice before determining the most efficacious dose for the patient. We will wait one week (7 days) before challenging the patient again. For example, if a patient is currently taking 20mg daily (10mg BID) and starts experiencing adverse reactions when taking 30mg daily, we will ask the patient to reduce the dose back down to 20mg daily for one week before attempting to take 30mg again. If the patient experiences adverse reactions again, we will repeat the same procedure once more and have the patient remain at the lower dose for another week (7 days) before challenging the patient again at 30mg. At this point, the PI will make the determination to leave the patient on the lower dose or proceed with the higher dose.

If a patient is unable to tolerate the lowest dose of medication (10mg QD), sites should ask the patient if they are willing to complete the study as scheduled so that we may obtain important study data. If the patient is unwilling, an early termination visit should be performed that will match the Week 36 visit.

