#### **4. Premature discontinuation, protocol violation or loss to follow-up**

All attempts will be made to enhance patient compliance. Early withdrawal may occur for any of the following reasons: a) the patient requests to; b) the investigator decides that it is in the patient's interest; c) a serious adverse event that is related to study medication; d) there is any other reason at the investigator's discretion. If the patient withdraws early, the patient will be encouraged to continue with scheduled visits. If they choose to not return, termination evaluations will be completed. If a patient is unable to return to the center, attempts will be made to follow the patient via telephone calls to complete the ALSFRS-R, adverse events and con meds until study completion.

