#### *Recording Adverse Events*

*Definition* - adverse events are clinical abnormalities (illness, signs, or symptoms) that begin or worsen during the course of the study and are not thought to be directly related to the expected course of ALS itself, whether or not the abnormality is believed by the investigator to be related to the study medication.

*Recording* - the investigator will monitor each patient closely and record all adverse events on the adverse event page of the case report form.

*Expectedness* - the investigator will determine whether the AE is expected or unexpected

*Severity* - adverse events should be graded for severity:

*Mild*: causing no limitation of usual activities

*Moderate*: causing some limitation of usual activities

*Severe*: causing inability to carry out usual activities

Adverse events should be followed up until they have stabilized or have returned to baseline status (in the event of a reaction to the medication). This is especially important for those events where the reported causal relationship to the study medication is anything other than “unrelated” (e.g. probable, possible). If patients have an adverse event that the PI assesses as “related” to the study medication then the PI will, or the patient can choose, to terminate the study or can decrease the dose of the medication by 10 mg per day. If the AE still does not abate then the PI or patient can again elect to terminate the study or decrease the dose by another 10 mg per day again. If the AE is still present after two dose titrations, then the patient must be terminated from the study. If the patient is terminated early, and the patient has not recovered from their adverse events, every effort should be made to follow the patient until the adverse event is resolved.

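### The adverse-event rule ends participation in the study, other sections keep such patients in follow-up, and no text links the two (minor, cheap to fix)

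*Combined protocol and SAP*

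**What the plan says.** Four places in the protocol bear on a patient who does not tolerate study drug.

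- **II.F, Recording Adverse Events:** "If the AE is still present after two dose titrations, then the patient must be terminated from the study". What follows concerns only follow-up of the event until it resolves.
- **II.C, Dosing Reduction/Discontinuation, first paragraph:** "If the AE is still present, intolerable or medically unsafe after two dose titrations, then the patient must be terminated from the study". Again only the event is to be reported and followed.
- **II.C, Dosing Reduction/Discontinuation, last paragraph,** for a patient who cannot tolerate 10 mg once daily: "sites should ask the patient if they are willing to complete the study as scheduled so that we may obtain important study data". Then: "If the patient is unwilling, an early termination visit should be performed that will match the Week 36 visit".
- **II.D.4, Premature discontinuation, protocol violation or loss to follow-up.** The reasons for early withdrawal include the investigator's decision and "c) a serious adverse event that is related to study medication; d) there is any other reason", the last at the investigator's discretion. Then: "If the patient withdraws early, the patient will be encouraged to continue with scheduled visits". For patients who can no longer attend in person: "attempts will be made to follow the patient via telephone calls to complete the ALSFRS-R, adverse events and con meds until study completion".

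The second paragraph of Dosing Reduction/Discontinuation adds a re-challenge route: "we will challenge the higher dose twice before determining the most efficacious dose for the patient".

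In II.C, Statistical Methods, the primary model is fitted to the ALSFRS-R scores of the 90 patients over the 36 weeks. Its restrictions are at patient level: at least one dose and at least two measurements. None removes a score because the patient had stopped drug.

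**The concern.** The plan uses one term, termination from the study, without separating the end of study medication from the end of outcome collection. The last paragraph of Dosing Reduction/Discontinuation contrasts completing the schedule with an early termination visit, so a site could fairly take *terminated* to mean that scheduled visits cease.

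The plan foresees 14 centers, and practice could differ between them. A patient handled under the literal rule would contribute at most one early-termination ALSFRS-R score after stopping, and the missed later scores cannot be recovered. The background section reports that, in other diseases, discontinuation tended to be higher on active drug, so the loss could fall more on the memantine arm. It gives no rate for ALS or for this trial.

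**Working it through.** **1. The rules side by side**

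| Section | Trigger | Drug | ALSFRS-R afterwards |
|---|---|---|---|
| Recording Adverse Events | Event persists after two reductions | Ends with termination | Not mentioned |
| Dosing Reduction/Discontinuation, first paragraph | Event present, intolerable or unsafe after two reductions | Ends with termination | Not mentioned |
| Same section, last paragraph | 10 mg once daily not tolerated | Not stated; stopping is implied | Patient asked to complete the schedule |
| II.D.4 | Early withdrawal, broad reasons | Not stated | Visits encouraged, otherwise telephone |

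No sentence ranks these rules or refers from one to another.

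**2. Two patients traced through the rules**

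- Starting from 30 mg/day, two 10 mg reductions give 30 − 10 − 10 = 10 mg/day. If the event is still not tolerated, the first paragraph requires termination and the last paragraph asks the patient to complete the study. This is a direct conflict.
- Starting from 40 mg/day, the result is 40 − 10 − 10 = 20 mg/day. The last paragraph does not apply, so outcome follow-up depends on whether II.D.4 covers the case.

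The steps before termination also differ. Remaining on the same dose is an option in Dosing Reduction/Discontinuation but not in Recording Adverse Events.

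**3. Scores at risk**

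ALSFRS-R is scheduled at screening and every 4 weeks from week 4 to week 36, which is 10 scores. A patient stopped at week 8 has 7 still to come (weeks 12 to 36). One stopped at week 12 has 6.

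**4. Scale, checked against the plan's stated power of 82%**

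- The placebo slope is −0.89 points/month, 95% CI −0.95 to −0.83, n = 415 (Results of Open Label Trial). Implied slope SD = (0.06/1.96) × √415 = 0.624.
- Planned effect (40%) = 0.40 × 0.89 = 0.356 points/month.
- SE with 30 v 60 patients = 0.624 × √(1/30 + 1/60) = 0.139.
- Power at two-sided 10% = Φ(0.356/0.139 − 1.645) = about 82%. This agrees with the plan.

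**5. Illustration of size**

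These are expected estimates from the planned mixed model (common intercept, placebo slope, slope change) with scores every 4 weeks. Assumed, because the documents do not give them: intercept SD 5.5, residual SD 2.0, slope SD 0.55 (0.62 as alternative), and stopping at week 8 or 12 in the memantine arm only, with decline at the placebo slope afterwards. The SE is 0.134 (0.148 with the alternative), which brackets the 0.139 above.

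| Stopping | Not followed | All followed | Gap | Gap / 0.134 |
|---|---|---|---|---|
| 5% (3 of 60) | 0.356 | 0.341–0.343 | 0.013–0.015 | about 0.1 |
| 10% (6 of 60) | 0.356 | 0.326–0.331 | 0.025–0.030 | about 0.2 |

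The gap is a bias only if the target includes time off drug. For an on-drug target, 0.356 is the right answer under these assumptions.

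**6. If the drug has no effect**

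Suppose terminated patients decline 0.4 points/month faster in either arm. Not following them shifts the slope difference towards memantine by 0.027–0.034 with 10% v 0% terminated (memantine v placebo), by 0.013–0.017 with 10% v 5%, and by zero at equal rates.

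**The case against.** The strongest reply is that II.D.4 already settles the matter. Its heading is general and its reasons are wide enough to take in an adverse-event termination. Recording Adverse Events is about events, so its silence on ALSFRS-R is unsurprising. At 10 mg/day, the last paragraph of Dosing Reduction/Discontinuation can be read as a specific rule that qualifies the general one. Most of this stands, and it is why the point is minor. What remains is that the termination sentences are mandatory, the follow-up sentences only ask or encourage, and no cross-reference joins them.

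A reader might infer that the primary analysis itself is undefined for scores taken after drug is stopped. The documents do not support that. Statistical Methods takes the patients' ALSFRS-R data over 36 weeks and lists its restrictions, none of which depends on drug status. The background description of the primary outcome does refer to progression on active therapy, but this may simply name the arm. The text leans towards using all collected scores and lacks only an explicit sentence.

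A reader might also take the 20–25% in the background section as a stopping rate and infer a large loss of power. That figure is the frequency of dizziness in studies of other diseases. No discontinuation rate is given, so no power loss can be attributed to this trial.

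**Conclusion.** The point holds as a minor inconsistency in the follow-up rules. Followed literally, the termination rule loses primary-outcome scores that other sections of the same protocol set out to collect. For a patient reduced from 30 to 10 mg/day the rules contradict each other outright.

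The effect on the result is unknown and may be near zero. The 0.1–0.2 standard errors rest on assumed stopping of 5–10% in one arm, at week 8–12, with benefit ending at once. With no drug effect, bias arises only if terminations differ between the arms in rate or in prognosis. If sites already treat II.D.4 as the general rule, little or nothing is lost.

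**What to change.** - Reconcile Dosing Reduction/Discontinuation, II.D.4 and Recording Adverse Events so that the end of study medication is separate from the end of outcome follow-up, and define *terminated* accordingly.
- State that II.D.4 (scheduled visits, or telephone ALSFRS-R, to week 36 unless consent is withdrawn) applies to patients stopped under the adverse-event rule.
- The differing reduction, re-challenge and termination steps must be reconciled by the investigators. No clinical rule is proposed here.
- As a clarification only, confirm in one sentence of Statistical Methods that all collected scores enter the primary model, with an on-drug analysis as sensitivity.

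**Cost:** protocol wording and one analysis sentence. Telephone ALSFRS-R is already scheduled at weeks 8, 16, 20, 28 and 32. A stopped patient who no longer attends would need up to three more calls (weeks 12, 24 and 36), which II.D.4 already foresees. If benefit ends with the drug, the added scores dilute the estimate somewhat, as the illustration shows.

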### ***Reporting of Serious Adverse Events (Immediately Reportable)***

#### *Serious Adverse Events*

*Definition*: Serious adverse events are life threatening, fatal, result in hospitalization or prolonged hospitalization, permanent disability, congenital anomaly, cancer, or overdose, or are any event that the investigator believes is very unusual or potentially serious.

*Report*: Any serious adverse event will be reported immediately (within 24 hours). All serious adverse events will be recorded on the standard adverse events page of the case report form, and a serious adverse event form will be completed. The coordinating center will be notified within 24 hours.

*Follow-up of Adverse Events*: The site investigator is responsible for appropriate medical management and laboratory tests for adverse events until the event is resolved. The management and resolution of each adverse event should be recorded on the adverse event page of the case report form.

Any clinical AE or abnormal test value that is serious (defined as fatal or life-threatening, one which results in inpatient hospitalization, one which results in persistent disability, congenital anomaly or is medically significant or requires intervention to prevent one of the other outcomes listed), and which occurs during the course of the study, regardless of the treatment group, must be reported within one working day of the investigator becoming aware of the event. In addition, for fatal and life threatening events, the Medical Monitor ([name] at the University of Kansas Medical Center) should be contacted immediately. The chair of the Data and Safety Monitoring Board ([name], Neurologist at University of Buffalo), and the DSMB, will review SAEs in a similar manner and make a determination if the patient can continue in the trial. If the subject needs to stop study medication [name] will contact the PI and study coordinator at that subjects' site.

**STUDY TABLE:**

Procedures	V1 SC	V2 BL	V3 Wk 4	V4 Wk 8	V5 Wk 12	V6 Wk 16	V7 Wk 20	V8 Wk 24	V9 Wk 28	V10 Wk 32	V11 Wk 36	V12 Wk 40
Consent	X											
Eligibility (Inclusion/Exclusion)	X											
Vitals	X		X		X			X			X	
Height	X											
Labs/Urine pregnancy test	X		X		X			X			X	
Med History	X											
Physical Exam	X		X		X			X			X	
FVC	X		X		X			X			X	
ALSFRS-R	X		X	X	X	X	X	X	X	X	X	
ALS-CBS	X		X		X			X			X	
NPI-Q	X		X		X			X			X	
C-SSRS	X		X		X			X			X	
Biomarkers	X		X		X			X			X	
Phone call				X		X	X		X	X		X
Drug dispensing		X	X		X			X				
Drug Acct			X		X			X			X	
Adverse Events			X	X	X	X	X	X	X	X	X	X
Concomitant Medication	X		X	X	X	X	X	X	X	X	X	X
Physician	X		X		X			X			X	
Study Coordinator	X		X	X	X	X	X	X	X	X	X	X
Data Entry	X		X	X	X	X	X	X	X	X	X	X
